5.3. Other Secondary Objectives

The other secondary objectives of the study are:

- To evaluate the efficacy of 2 doses of dasotraline (4 and 6 mg/day) compared with placebo in adults with moderate to severe BED as measured by:
 - Number of binge episodes per week
 - Proportion of binge eating responders at Week 12 who show $\geq 75\%$ reduction in the number of binge eating episodes
 - Sheehan Disability Scale (SDS)
 - Montgomery-Asberg Depression Rating Scale (MADRS)
 - Hamilton Anxiety Rating Scale (HAM-A)
 - Eating Disorder Examination Questionnaire (EDE-Q) modified
- To evaluate the safety and tolerability of 2 doses of dasotraline (4 and 6 mg/day) using physical examinations, 12-lead electrocardiograms (ECG), vital signs, AE reports, clinical laboratory results, body weight, body mass index (BMI), and Columbia – Suicide Severity Rating Scale (C-SSRS)

- To assess potential withdrawal effects upon abrupt discontinuation of dasotraline after 12 weeks of continuous daily treatment using the following assessments (administered during the withdrawal period):
 - Cocaine Selective Severity Assessment (CSSA)
 - Discontinuation-Emergent Signs and Symptoms (DESS) Scale
 - Symptoms of anxiety utilizing the HAM-A
 - Symptoms of depression utilizing the MADRS
- To assess the abuse potential of dasotraline utilizing a comprehensive abuse potential monitoring plan (APMP)
- To assess the relationship between dasotraline plasma concentration and the primary efficacy and selected secondary efficacy and safety endpoints

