2.3. Other Secondary Objective

The other secondary objectives of the study are:

- To evaluate the efficacy of 2 doses of dasotraline (4 and 6 mg/day) compared with placebo in adults with moderate to severe BED as measured by:
 - Number of binge episodes per week
 - Proportion of binge eating responders at Week 12 who show $\geq 75\%$ reduction in the number of binge eating episodes
 - Eating Disorder Examination Questionnaire (EDE-Q) modified
 - Sheehan Disability Scale (SDS)
 - Montgomery-Asberg Depression Rating Scale (MADRS)
 - Hamilton Anxiety Rating Scale (HAM-A)
- To evaluate the safety and tolerability of 2 doses of dasotraline (4 and 6 mg/day) using physical examinations, 12-lead electrocardiograms (ECG), vital signs, adverse event (AE) reports, clinical laboratory results, body weight, body mass index (BMI), and Columbia – Suicide Severity Rating Scale (C-SSRS)
- To assess potential withdrawal effects upon abrupt discontinuation of dasotraline after 12 weeks of continuous daily treatment using the following assessments (administered during the withdrawal period):
 - Cocaine Selective Severity Assessment (CSSA)
 - Discontinuation-Emergent Signs and Symptoms (DESS) Scale
 - Symptoms of anxiety utilizing the HAM-A
 - Symptoms of depression utilizing the MADRS

321

- To assess the abuse potential of dasotraline utilizing a comprehensive abuse potential monitoring plan (APMP)
- To assess the relationship between dasotraline plasma concentration and the primary efficacy and selected secondary efficacy and safety endpoints

3. Study Design

This is a randomized, double-blind, parallel-group, multicenter, outpatient study evaluating the efficacy and safety of 2 doses of dasotraline in adults with BED using dasotraline (4 and 6 mg/day) versus placebo over a 12-week treatment period. This study is projected to randomize approximately 480 subjects to 3 treatment groups in a 1:1:1 ratio (4 mg/day dasotraline, 6 mg/day dasotraline and placebo). Subjects randomized to placebo receive placebo for the duration of the treatment throughout the study. Subjects randomized to 4 mg/day dasotraline receive 4 mg/day for the duration of the treatment period. Subjects randomized to 6 mg/day dasotraline are dosed with 4 mg/day dasotraline for the first 2 weeks of the treatment period and are increased to 6 mg/day at Week 2.

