6.1.1.2. Withdrawal Period (Off Treatment)

For subjects who either are early terminated from DB period or complete DB period but do not enter the extension, withdrawal period analyses will be generated; no withdrawal period analyses will be produced for subjects entering the extension study.

The withdrawal period will begin with immediately after the last study dose. Study day relative to the last study dose date will be denoted as Day 0. The end of the withdrawal period is defined as the maximum of last study visit (scheduled or unscheduled) and last phone contact after the

321

last study dose. If the last study dose date is missing (eg, lost follow-up subjects), start and end days will be set as missing.

Each subject’s assessment at each visit (site or phone contact) in the withdrawal period will be assigned a study day with respect to start date of the withdrawal period.

- Study Day = Assessment date – start date of the withdrawal period if assessment date \geq start date of the withdrawal period

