6.1.9 Analysis Populations

The Intent-to-Treat (ITT) Population: All randomized subjects who receive at least one dose of study medication and have at least 1 post-baseline result in any efficacy evaluation. The ITT population is the primary population for efficacy analyses, ie, unless otherwise specified, all efficacy analyses are based on ITT population.

The Per Protocol (PP) Population: All ITT subjects who have no major protocol violations that may affect the interpretation of the primary efficacy endpoint. The PP population will be used to assess robustness of the primary efficacy analysis. Major protocol violations and the PP population will be determined through a blinded data review meeting (BDRM) and identified prior to the database lock.

Subjects in the ITT and PP populations will be analyzed based on the treatment to which they are randomized.

The Double-blind (DB) Safety Population: All randomized subjects who receive at least one dose of study medication. The DB safety population mainly is used for the data analyses of the safety data collected through Week 12 or during the treatment period. Subjects are analyzed based on the actual treatment received; specifically, for subjects who are randomized to dasotraline 6 mg group and dosed with dasotraline 4 mg but never titrated to dasotraline 6 mg (ie, early terminated on or prior to Week 2 visit), the actual dose will be dasotraline 4 mg; otherwise, actual dose will be set as dasotraline 6 mg; In the event that a subject receives a treatment other than the one to which he/she is randomized or expected, the actual treatment is defined as the treatment to which the subject is exposed for the greatest duration during the treatment period. The actual treatment is generally the same as the randomized treatment group, unless the subject takes incorrect/unexpected dose during the entire study. Hereafter, DB safety population will be referred as safety population by default.

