The Withdrawal Population: The withdrawal population includes all randomized subjects who receive at least one dose of study medication, and either discontinues the study drug during the treatment period before the Week 12 visit or completes the 12-week treatment period but do not enter the extension study (Study SEP360-322), and have at least 1 assessment after the last study drug for any safety or efficacy evaluation. The withdrawal population mainly is used to summarize the safety/efficacy assessments collected in the withdrawal period except of adverse event data.

The Modified Withdrawal Population: all subjects in the withdrawal population plus the subjects who do not enter the extension study and do not enter the withdrawal period, but the last study dose dates are at least 2 days earlier than the last study visit. The modified withdrawal population will be mainly used for adverse event that could be retrospectively collected.

Withdrawal analyses will be presented by planned treatment group for efficacy data and by actual treatment group for safety data.

Pharmacokinetics (PK) Population: The PK population is defined as all subjects who are randomized, receive at least 1 dose of study drug, and have any post-baseline plasma concentrations sample collection of dasotraline.

6.1.10 Stratification Factor ‘Baseline Number of Binge Days’ vs. Baseline Number of Binge Days Group

Group of Baseline number of binge days is defined as: Baseline number of binge days ≤ 4 , Baseline number of binge days >4 ; this group should be essentially equivalent to the stratification factor unless there is a subject stratified into the incorrect stratum. The stratification factor (ie, Baseline binge days category) will be consistently used in the statistical models, when applicable, for efficacy analysis as described in this document. Compared with the stratification factor, group of Baseline number of binge days will be used in the other scenarios, including the statistical models based analyses for safety variables.

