7.4 Safety

7.4.1 Analysis Specifications

Safety reporting includes all safety data reported during the 12-weeks double-blind treatment period, as well as the all safety data reported in post-treatment withdrawal period, if a subject does not enter the extension study.

The safety data will be analyzed by treatment group based on the safety population for data up to the end of treatment period and on the withdrawal population for data collected during the withdrawal period, separately, as appropriate. Specifically, the data, which are used to assess physical dependence and withdrawal symptoms, will be analyzed by treatment for data collected in the withdrawal period based on the modified withdrawal population for AE, CSSA and DESS, and based on withdrawal population for MADRS and HAM-A, respectively. Unless otherwise specified, for continuous data collected in the treatment period, the actual value and change from baseline (ie, DB baseline) will be summarized by treatment and visit; for continuous data collected in the withdrawal period, the actual value, change from DB baseline (when applicable), and change from withdrawal baseline will be summarized by treatment and visit.

There will be no imputation of missing values for clinical laboratory test results, vital sign measurements, and ECG evaluations in the by-visit analyses. All analyses of safety data are descriptive. No inferential analyses of safety data are performed.

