7.4.6 Assessments of Withdrawal Effects (CSSA, DESS, HAM-A, and MADRS)

CSSA total score, DESS total score, MADRS total score, and HAM-A total score will be summarized by presenting descriptive statistics (N, mean, median, and range) of observed values and change from withdrawal baseline by treatment and visit (ie, both clinic and non-clinic visits) for the withdrawal period.

A similar analysis will be performed by gender as well.

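### The withdrawal objective concerns stopping after 12 weeks of treatment, but every planned summary of CSSA, DESS, HAM-A and MADRS pools early discontinuers with 12-week completers and none isolates the 12-week group.

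*SAP*

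**What the plan says.** The objective is worded the same way in both documents. Protocol 5.3: "To assess potential withdrawal effects upon abrupt discontinuation of dasotraline after 12 weeks of continuous daily treatment using the following assessments", followed by CSSA, DESS, HAM-A and MADRS. SAP 2.3 repeats "withdrawal effects upon abrupt discontinuation of dasotraline after 12 weeks of continuous daily treatment".

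The analysis set is broader. The withdrawal population in SAP 6.1.9 includes a dosed subject who "either discontinues the study drug during the treatment period before the Week 12 visit or completes the 12-week treatment period" but stays out of the extension, given at least one assessment after the last dose. The modified withdrawal population adds some further subjects and has no minimum exposure. SAP 7.4.1 assigns the scales to these sets: "based on the modified withdrawal population for AE, CSSA and DESS, and based on withdrawal population for MADRS and HAM-A". SAP 7.4.6 then gives descriptive statistics of "observed values and change from withdrawal baseline by treatment and visit (ie, both clinic and non-clinic visits) for the withdrawal period", repeated by gender.

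The protocol set this up. Section 6.4 defines the endpoint as change from Week 12/EOT, section 13.3 asks early discontinuers to complete the withdrawal visits, the Withdrawal Safety Population in section 15.3 includes them, and sections 15.4.2 and 15.4.2.7 summarise the four scales in that population by treatment and visit.

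Subjects who enter the extension are left out: "no withdrawal period analyses will be produced for subjects entering the extension study" (SAP 6.1.1.2). Under protocol 7.1 and 11.8.9 only subjects who completed the 12 weeks can enter it.

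**The concern.** The objective names a specific exposure: 12 weeks of daily dosing, then an abrupt stop. The planned columns mix subjects with that exposure and subjects who may have stopped after a few days. The extension removes subjects only from the completer side, so the higher its uptake, the smaller the share of each column that has the exposure the objective names.

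At stake is how directly the trial can report on that objective. A reader of the planned tables would see a mean over a mixed group and could not tell what the 12-week subjects showed. The disposition table (SAP 7.1.3) gives counts of completers, extension entrants and discontinuations, but no scores. The split could be made afterwards from listings, but it would then not be prespecified.

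**Working it through.** **Step 1: compare the objective with each summary rule.**

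| Place | Population or grouping | Split by completion or time on drug? |
|---|---|---|
| Protocol 5.3, SAP 2.3 | objective: stop after 12 weeks of daily treatment | names the 12-week group |
| Protocol 15.3, 15.4.2, 15.4.2.7 | early discontinuers and non-extension completers, by treatment and visit | no |
| SAP 6.1.9 | withdrawal and modified withdrawal populations, both pooled | no |
| SAP 7.4.1 | CSSA and DESS in the modified set; MADRS and HAM-A in the withdrawal set | no |
| SAP 7.4.6 | treatment, visit, then gender | no |
| SAP 7.4.2 | discontinuation-emergent adverse events by withdrawal duration | no: counts days since last dose, not time on drug |

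No section in the text supplied isolates the 12-week group for these scales. The SAP attachments are not in that text; those cited in the SAP body concern other topics.

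**Step 2: illustrate the mix.** Inputs from protocol 15.1 and SAP 3.1: 96 subjects per group needed, about 40% allowance for discontinuation, 160 randomised per group. Reading the 40% as the share of randomised subjects who discontinue reproduces the plan's figure: 96 / (1 − 0.40) = 160. Per arm this gives 160 × 0.40 = 64 early discontinuers and 160 − 64 = 96 completers.

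The documents give neither extension uptake nor the share of early discontinuers who are assessed afterwards. Both are assumed here (uptake 0% to 90%; 50% to 100% of early discontinuers assessed), as is an equal 40% in each arm. All non-extension completers are taken as assessed.

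Completer share = 96 × (1 − uptake) / [96 × (1 − uptake) + early discontinuers assessed].

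| Extension uptake | Completers left | Share if 64 assessed | Share if 32 assessed |
|---|---|---|---|
| 0% | 96 | 96/160 = 60% | 96/128 = 75% |
| 50% | 48 | 48/112 = 43% | 48/80 = 60% |
| 75% | 24 | 24/88 = 27% | 24/56 = 43% |
| 90% | 9.6 | 9.6/73.6 = 13% | 9.6/41.6 = 23% |

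**Step 3: change scores.** These also need a withdrawal baseline inside the window in SAP Table 6.1 (Day −5 to 1 for CSSA and DESS, −5 to 3 for the others), and SAP 6.1.2.4 does not impute a missing one. Suppose, again as an assumption, that all completers but only half of the assessed early discontinuers (16 to 32) have one. The completer share of change scores then runs from 9.6/(9.6 + 32) = 23% to 96/(96 + 16) = 86%.

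The shares are by randomised arm, whereas the safety tables use actual treatment. They show only that the mix could lie almost anywhere. They say nothing about scores.

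**Step 4: precision of a separate column.** The 95% CI half-width for a mean change, in SD units, is t(0.975, n − 1)/√n: 1.985/√96 = 0.20, 2.012/√48 = 0.29, 2.262/√10 = 0.72.

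**The case against.** The strongest reply is that the SAP does what the protocol prescribes. Early discontinuers are sent into the withdrawal period on purpose, with visits timed from their own last dose (protocol 11.8.10), and the endpoint is change from Week 12/EOT. On that view the phrase about 12 weeks merely describes the planned treatment period, and rewording the objective would remove the mismatch without any new table. This stands as far as intent goes: the pooling is no error and no departure from the protocol. It does not supply a summary of the group both documents name.

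Second, early discontinuers may be informative. With the half-life of 47.1 to 77.0 hours in protocol 4.2 and the usual five-half-life convention (an assumption), steady state takes 5 × 47.1/24 = 9.8 to 5 × 77.0/24 = 16.0 days, so many could be near it when they stop. That is a good reason to keep the pooled tables and to show this group as well.

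Third, a completer column does not match the objective exactly. Completing the Week 12 visit is not the same as dosing every day, since protocol 10.2 counts a subject as noncompliant only above 25% missed doses, and subjects who go on to the extension supply no withdrawal data. This also stands. The column is the closest available summary and should be described that way.

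A reader might also object to the treatment labels. SAP 6.1.9 says "Withdrawal analyses will be presented by planned treatment group for efficacy data and by actual treatment group for safety data", and for 6 mg subjects "never titrated to dasotraline 6 mg (ie, early terminated on or prior to Week 2 visit), the actual dose will be dasotraline 4 mg". It is tempting to see this as contaminating the 4 mg column. The documents do not support that: those subjects took only 4 mg, so the label reflects the dose received.

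**Conclusion.** The point holds as a gap in presentation. The objective names subjects stopping after 12 weeks, and every planned summary of the four scales pools them with early discontinuers. This rests on the wording of the two documents and needs no numerical assumption.

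Two stronger conclusions do not follow. A reader might infer that no planned table addresses the objective; in fact the non-extension 12-week subjects are in the planned tables and are simply not shown separately. A reader might also infer that pooling biases or dilutes the withdrawal signal. The documents give no scores by length of exposure, no extension uptake and no return rate, so neither size nor direction can be stated. The 13% to 75% range describes the possible mix under assumed shares.

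The practical weight is modest. The summaries are descriptive, no hypothesis test or multiplicity step depends on them, and subject listings (SAP 6.2.1) would allow a later split. This is a cheap improvement for the sponsor to consider.

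**What to change.** Keep the pooled tables. In SAP 7.4.6 add prespecified descriptive columns for the four scales, at withdrawal baseline and Weeks 13, 14 and 15, by treatment:

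- (a) subjects who completed 12 weeks and did not enter the extension, described as the summary closest to the objective and flagged as a subset selected after randomisation;
- (b) early discontinuers.

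For each column, report the number with an in-window withdrawal baseline. The split need not be repeated by gender or for the 13 phone-contact windows in SAP Table 6.2.

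Cost: a few lines of SAP text, one grouping variable from completion and extension status already used in SAP 7.1.3, and a few tables. That is 4 scales × 4 time points = 16 rows of observed values per column and arm, of which 4 × 3 = 12 also carry a change score. No new data are needed. The downside is that some columns may be small: at 10 subjects a mean change would have a 95% CI half-width of about 0.72 SD, against 0.29 SD at 48.

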6.1.11 Handling of Dropouts or Missing Data

6.1.11.1 Missing Diary Entry

Missing diary on certain assessed days in an assessment period will not be imputed, see [Section 5.1.1.1](#).

6.1.11.2 Unknown or Unconfirmed Last Study Dose Date

If the end date of the medication intake is unknown or ‘unconfirmed’ (including but not limited to, eg, subject is lost to follow-up), it will be imputed as the earlier of the disposition date (ie, date of the last contact with subject) and 7 days from the date that the last medication kit is dispensed.

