Baseline Visit (Day -1): Subjects who meet eligibility criteria at Screening will return to the study site on Day -1 for confirmation of screening evaluations as well as completion of predose assessments and procedures including clinician review of the daily binge eating diary. Any lapse in diary completion during the 14 day period (eg, 1 or more days are skipped) will be discussed with the subject. If 1 or 2 days per week are incomplete or missing, the subject may complete the diary with the clinician. However, if the subject cannot recall enough information to complete the diary in full after clinician review, the subject will be ineligible. Subjects will also be ineligible for randomization if there are more than 2 missed diary days in 1 week. Eligible subjects (based on confirmation of study entry criteria) will be randomized and dispensed study drug at Day -1.

Treatment Period (Day 1 [Week 0] through Day 84 [Week 12]): Subjects will self-administer the study drug on an outpatient basis once a day with or without food beginning on Day 1, the day after the Baseline visit, and continue for 12 weeks. Subjects will be instructed to administer study drug at approximately the same time each morning including on days when clinic visits occur. During the treatment period subjects will continue to complete a daily binge eating diary, which will be reviewed at each visit. During the treatment period, subjects will have one clinic visit every week for the first month, then one clinic visit every 2 weeks thereafter. In order to facilitate scheduling of clinic visits, a window of ± 2 days will be allowed for each weekly clinic visit and a window of ± 3 days will be allowed for each biweekly clinic visit, and a window of ± 1 day for the end of treatment (EOT) visit and each clinic visit of the withdrawal period.

Subjects who complete the 12-week Treatment Period may be eligible for participation in the open label extension study (SEP360-322). For subjects enrolling in the open label extension study, Week 12 will be the last visit for this study.

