7.2. Treatment Assignment and Blinding

7.2.1. Treatment Assignment

After successfully meeting study entry criteria, subjects will be randomly assigned in a 1:1:1 ratio to 1 of 3 treatment arms:

- Dasotraline 4 mg/day
- Dasotraline 6 mg/day
- Placebo

To avoid potential imbalanced treatment allocation among subjects with different baseline levels of BED, the randomization will be balanced using permuted blocks with baseline number of binge eating days per week, which is defined as number of binge days/week determined from the 2 weeks before the Baseline visit (3 – 4 binge eating days per week, > 4 binge eating days per week). The stratification process will be handled by an IXRS, an integrated web-based subject and drug-management system.

An IXRS will be used to manage randomization at Day -1 and, if necessary, for emergency unblinding (see [Section 7.2.3](#)) of treatment assignment during the study.

Study medication will be assigned by an IXRS at Day -1 based on the randomization schedule. The IXRS will generate instructions on which medication number to assign to a subject. Each randomized subject will be dispensed one 10-day blister pack per scheduled visit up to and including Visit 5 and two 10-day blister packs per scheduled visit thereafter through Visit 9.

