9.2. Study Drug Packaging and Labeling

9.2.1. Package Description

Study drug will be provided in 1-week blister cards containing 10 capsules of dasotraline 4 mg or 6 mg capsules or placebo capsules (7 days + 3 extra days).

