7.4.2 Adverse Events

All AEs are coded using Medical Dictionary for Regulatory Activities (MedDRA) version 18.0 or higher.

Treatment-Emergent Adverse Event (TEAE)

A treatment-emergent adverse event (TEAE) is defined as an AE with a start date on or after the date of first dose through 7 days after study drug discontinuation (14 days for serious adverse events and deaths) for subjects who complete or discontinue this study but do not enter into the extension study), or through the last study day of the double-blind treatment period for subjects

continuing into the extension study (ie, subjects in safety population). AEs with a start date prior to initiation of double-blind study medication which are reported to have an increase in intensity, or which are reported to have a attribution in relationship to study medication (ie, attribution to possible related, probably related, related) after the initiation of double-blind study medication are considered as TEAEs.

Discontinuation-emergent adverse event (DEAE) is defined as an AE with a start date after the last dose day of study medication through the last study visit in the withdrawal period.

Table summary of overall AEs (and SAEs) will be limited to TEAEs and DEAEs. All AE data will be displayed in data listings. For sake of simplicity, hereafter TEAE is referred as AE in this section.

The overall incidence (ie, number and percent of subjects with one or more AE in each category) of AEs, serious AEs, deaths, AEs leading to discontinuation, study drug-related AEs, serious study drug-related AEs, study drug-related AEs leading to discontinuation, and serious AEs leading to discontinuation, serious study drug-related AEs, will be summarized by treatment group.

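### The 7-day cap on an imputed last-dose date fits weekly dispensing only; after a Visit 6–9 dispensing it may place the last dose up to 7 days too early

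*SAP*

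**What the plan says.** **The rule.** SAP 6.1.11.2 covers last-dose dates that are unknown or unconfirmed; loss to follow-up is given only as an example. The imputed date is the earlier of the date of last contact and "7 days from the date that the last medication kit is dispensed". The rule does not vary by visit.

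**The supply.** Protocol 7.2.1 dispenses "one 10-day blister pack per scheduled visit up to and including Visit 5", then "two 10-day blister packs per scheduled visit thereafter through Visit 9". Protocol 9.2.1 describes the packs as "1-week blister cards containing 10 capsules", that is, 7 scheduled days plus 3 spare. Protocol 7.1 schedules "one clinic visit every week for the first month, then one clinic visit every 2 weeks thereafter", and "a window of ± 3 days will be allowed for each biweekly clinic visit".

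**Where the date is used.**
- Treatment duration: SAP 7.1.5, which points to the imputation rule under the number 6.1.9.2, evidently meaning 6.1.11.2.
- The treatment-emergent (TEAE) window for subjects who do not enter the extension: "through 7 days after study drug discontinuation", or 14 days for serious events and deaths (SAP 7.4.2).
- Discontinuation-emergent (DEAE) status, which starts the day after the last dose (SAP 7.4.2).
- Day 0 of the withdrawal period (SAP 6.1.1.2) and the visit windows in SAP Table 6.1.

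**Two other rules for the same situation.** When the end of medication intake is unknown, SAP 6.1.1.1 ends the double-blind period at the withdrawal date supplied by the site. When the last-dose date is missing, SAP 6.1.1.2 sets the start and end of the withdrawal period to missing.

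**The concern.** The cap equals the whole planned dosing interval at weekly visits but only half of it at biweekly visits, and no reason is given. The biweekly visits are 4 of the 8 dispensing visits (Visits 6–9 out of 2–9) and cover Weeks 4 to 12, which is 8 of the 12 treatment weeks.

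An imputed date that is too early shortens recorded exposure. It also moves the start of the withdrawal period into time when the subject may still have been taking drug, and this study sets out to measure withdrawal effects from the last dose. The direction also sits poorly with SAP 6.1.11.4.1, which takes the conservative line for incomplete adverse event dates: if status cannot be determined, the event is treated as treatment-emergent.

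**Working it through.** **Inputs.** Dispensing falls on Days -1, 7, 14, 21, 28, 42, 56 and 70 (Visits 2–9), and Week 12 is Day 84 (Protocol Table 2). Packs per visit come from Protocol 7.2.1, and scheduled days per pack (7) from Protocol 9.2.1.

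**Step 1: where the 7-day figure fits.** Scheduled days supplied = packs × 7.

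| Dispensing visit | Packs | Scheduled days supplied | Interval to next visit | Cap | Shortfall |
|---|---|---|---|---|---|
| 2–5 | 1 | 1 × 7 = 7 | 7 | 7 | 0 |
| 6–9 | 2 | 2 × 7 = 14 | 14 | 7 | 14 − 7 = 7 |

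The cap reproduces for Visits 2–5 and does not for Visits 6–9.

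**Step 2: when the cap binds.** Let x be the days from a Visit 6–9 dispensing to last contact. The current rule gives dispensing + min(x, 7). A cap matched to the interval gives dispensing + min(x, 14).
- x ≤ 7: no difference. A subject never heard from after the dispensing visit (x = 0) is governed by last contact under either rule.
- 8 ≤ x ≤ 14: difference x − 7, that is, 1 day at x = 8, 3 at x = 10 and 7 at x = 14.
- x > 14: difference 14 − 7 = 7 days.

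**Step 3: exposure.** Kits dispensed on Day 70, subject seen on Day 84, last-dose date unconfirmed. The current rule gives 70 + 7 = Day 77; the matched cap gives 70 + 14 = Day 84. Duration = last − first + 1, so 77 − 1 + 1 = 77 days (the 70–82 category) against 84 days (the ≥83 category).

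**Step 4: withdrawal mapping, same subject, not entering the extension.** Withdrawal day = visit day − last-dose day.
- Current rule: 84 − 77 = 7. In Table 6.1 this is Withdrawal Week 1 (days 2–10 for CSSA and DESS, days 4–10 for other data).
- Matched cap: 84 − 84 = 0, which is Withdrawal Baseline.
- Under the current rule the dispensing visit is at 70 − 77 = −7, outside the baseline window that opens at −5. No scheduled clinic visit supplies a baseline, and SAP 6.1.2.4 does not impute one.
- Adverse events with onset on Days 78–84 fall after the imputed last dose and so count as DEAEs. They remain TEAEs as well, because 77 + 7 = 84.
- The double-blind period still ends on Day 84, the Week 12 visit, so it overlaps the withdrawal period on Days 78–84.

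**Step 5: TEAE status.** When the cap binds, the window closes at dispensing + 7 + 7 = 14 days, or + 7 + 14 = 21 days for serious events. Under the matched cap it closes as late as 14 + 7 = 21 and 14 + 14 = 28. If events are known only up to last contact, the onset days observed but excluded under the current rule are 0 for x ≤ 14, 1 at x = 15, 6 at x = 20 and 7 at x = 21. For serious events there are none until x exceeds 21.

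**The case against.** The strongest reply is that the rule takes the earlier of two dates. A subject who disappears after collecting drug gets the last-contact date, and changing the cap does nothing for that subject. This stands. The cap matters only when contact occurs 8 or more days after dispensing and the last dose is still unknown or unconfirmed. SAP 7.1.5 narrows the group further by accepting reported dosing dates even when cards are not returned.

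A reader might infer that adverse events in subjects still on drug drop out of the TEAE table. The documents do not support that for planned dosing: the window stays open to day 14 after dispensing, which covers the full 14-day interval. Only use of spare capsules (20 are supplied) could put an excluded onset on drug. For extension entrants the TEAE window does not run from the last dose at all, and every adverse event is listed regardless of status.

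It is also fair that the true last dose is unknown, so an early imputation may be right for someone who stopped early. And for subjects lost to follow-up, SAP 6.1.1.2 may set the withdrawal period to missing, so the mapping problem need not arise for them.

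One defence fails: that 7 days is a deliberate midpoint. At weekly visits 7 days is the full interval, so the rule is not a midpoint rule. None of these points explains why the cap ignores the number of cards dispensed.

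**Conclusion.** The mismatch is real and its effect is limited. After a Visit 6–9 dispensing with last contact 8 or more days later, the imputed last dose may be up to 7 days too early. What survives is possible understatement of treatment duration and, for subjects still seen with an unconfirmed date, a misplaced withdrawal baseline and double classification of events from Days 78–84. The withdrawal result assumes that an unconfirmed date is imputed under 6.1.11.2 before withdrawal days are counted; the SAP does not state the order.

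TEAE status changes only for onsets more than 14 days after dispensing, or 21 for serious events. Multiplying an assumed loss-to-follow-up rate by the number randomised would not give a count of affected subjects. It would include those lost before Week 4 and those last seen within 7 days of dispensing, and neither group is affected. The documents allow no estimate of the rest.

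The primary efficacy analysis does not use this date. The 28-day exposure criterion for the per-protocol population is also untouched where the shortfall applies: Visit 6 can fall no earlier than 28 − 2 = Day 26 within its window, and 26 + 7 = Day 33.

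**What to change.** In SAP 6.1.11.2, impute the earlier of the last-contact date and the last dispensing date plus the planned interval: 7 days for kits dispensed at Visits 2–5 and 14 days for kits dispensed at Visits 6–9. In the same edit, state which rule takes precedence when the last dose is unknown, unconfirmed or missing, so that 6.1.11.2 agrees with 6.1.1.1 (site withdrawal date) and 6.1.1.2 (set to missing). Correct the section number cited in 7.1.5.

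The cap needs one SAP sentence and one programming condition before database lock; the reconciliation is wording. The downside is slightly longer assumed exposure for some subjects who in fact stopped earlier.
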